4.3.1 Concomitant treatments

Information on any treatment in the 4 weeks prior to starting study treatment and all concomitant treatments given during the study, with reasons for the treatment, will be recorded in the Case Report Form (CRF). If medically feasible, patients taking regular medication, with the exception of potent inducers of CYP3A4 (see section 4.2 exclusion 1, and Appendix H), should be maintained on it throughout the study period.

Patients taking concomitant medications whose disposition is dependent upon BRCP and which have a narrow therapeutic index should be closely monitored for signs of changed tolerability as a result of increased exposure of the concomitant medication whilst receiving AZD9291. Patients taking warfarin should be monitored regularly for changes in prothrombin time or INR. Guidance on medications to avoid, medications that require close monitoring and washout periods should be provided (see Appendix H).

Patients taking rosuvastatin (due to BCRP mediated increase in exposure) should have CPK levels monitored. If the patient experiences any potentially relevant AE suggestive of muscle toxicity including unexplained muscle pain, tenderness, or weakness, particularly if accompanied by malaise or fever, the rosuvastatin must be stopped and any appropriate further management should be taken.

Concomitant use of regular medications that may prolong the QT interval will be restricted whenever feasible, but patients may receive any medication that is clinically indicated for the treatment of AEs (See Appendix H)

Prohibited Medication/Class of drug:	Usage:						
Other anticancer agents, investigational agents and radiotherapy	Should not be given while the patient is on study treatment. #see palliative radiotherapy in box below for exception						

Guidance on medications that require close monitoring is given on Appendix H.

Rescue/Supportive Medication/Class of drug:	Usage:
Pre-medication will be allowed after, but not before the first dose of study treatment.	To be administrated as directed by the investigator. This includes management of diarrhea, nausea and vomiting.
Blood transfusions	Allowed at any time during the study.

Rescue/Supportive Medication/Class of drug:	Usage:
Granulocyte colony stimulating factors	Should not be used prophylactically during Cycle 1. Use of prophylactic colony stimulating factors may be considered after Cycle 1 following discussion with the AstraZeneca Study Team Physician.
Corticosteroids and/or bisphosphonates	Patients may receive treatment with corticosteroids and/or bisphosphonates for the treatment of bone metastases.
Palliative radiation	Patients may receive radiotherapy for painful bony metastases.
Supportive care and other medications that are considered necessary for the patient's well-being	To be administered as directed by the investigator.

4.3.2 Other concomitant treatment

Other medication other than that described above, which is considered necessary for the subject's safety and well being, may be given at the discretion of the Investigator and recorded in the appropriate sections of the Case Report Form.

5. STUDY TREATMENT AND CONDUCT

5.1 Identity of investigational product(s)

AZD9291 is planned to be administered orally as a single daily dose (although alternative frequencies or intermittent schedules may be instigated in response to emerging safety, tolerability or PK data).

AstraZeneca will supply AZD9291 as tablets for oral dosing. Additional information about the investigational product may be found in the Investigators' Brochure.

Investigational product	Dosage form and strength	Manufacturer
AZD9291	40-80 mg Tablets	AstraZeneca

Tablets will be packed in high-density polyethylene (HDPE) bottles with child-resistant closures. One or more bottles of AZD9291 will be dispensed at each dispensing visit depending on the dose. Bottles will be dispensed to subjects in the AstraZeneca packing provided. The packaging includes bottles, caps and a label. Bottle tampers should not be broken prior to dispensing study drug to a patient.

Labels will be prepared in accordance with Good Manufacturing Practice and local regulatory guidelines. The labels will fulfil Good Manufacturing Practice Annex 13 requirements for labelling. Label text will be translated into local language.

The label will include the Name of the Sponsor, Study Code, For Clinical trial use only and /or any other market specific requirements.

All study drugs should be kept in a secure place under appropriate storage conditions. The investigational product label on the pack specifies the appropriate storage.

5.2 Dose and treatment regimens

AstraZeneca will supply AZD9291 as tablets for oral administration as a single daily dose of 40 mg and 80 mg respectively. At each dispensing visit, sufficient AZD9291 for 21 days treatment, plus overage, will be dispensed.

Patients will be administered a single dose of AZD9291 on Day 1, Cycle 0 at the beginning of Part A period. From Day 2 to Day 6, no treatment will be given, but PK samples will be obtained; on Day 8 (Cycle1, Day1), the patients will be administered AZD9291 on a continuous schedule. Part A treatment will complete at the end of Cycle 4 and treatment in Part B will continue.

Patients may continue receiving AZD9291 until treatment discontinuation criteria are met. Patients may receive AZD 9291 beyond disease progression as long as they are considered to receive clinical benefit continuously judged by the treating physician.

Patients who were started and have remained on treatment at a dose of 40mg for at least 6 months, have shown clinical benefit (as judged by the investigator) and have then developed RECIST confirmed disease progression, and did not experience any treatment – related grade 3 AE when treated at dose of 40mg, may have dose increased to 80mg after agreement in advance between the Investigator and AZ Study Physician. 80mg has been declared to have an acceptable tolerability profile by the Safety Review Committee.

Tablets should be taken whole with water, 240ml being the recommended volume for PK days. AZD9291 can be taken with or without food at the same time each day. Patients will be required to fast (water only) for at least 8 hours prior to the collection of a fasting glucose sample as per the study plan (Table 2).

Doses should be taken approximately 24 hours apart at the same time each day. Doses should not be missed. If a patient misses taking a scheduled dose, within a window of 12 hours, it is acceptable to take the dose. If it is more than 12 hours after the dose time, the missed dose should not be taken, and patients should be instructed to take the next dose at the next scheduled time. If a patient vomits after taking their AZD9291, they should not make up for this dose, but should take the next scheduled dose.

Any change from dosing schedule, dose interruptions, dose reductions should be recorded in the eCRF.

Assessment timings if dosing is interrupted

If a patient misses any doses of AZD9291 during the 21-day evaluation period of Cycle 1, please contact the AstraZeneca Study physician or site monitor for advice regarding the evaluability of the patient and appropriate timing of the PK assessments. All other assessments, including laboratory safety assessments, vital signs and RECIST should continue to be performed as per study plan, relative to the baseline assessments.

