5.2.1 Toxicity management

If a patient experiences a CTCAE grade 3 or higher and/or unacceptable toxicity (any grade) not attributable to the disease or disease-related processes under investigation, where the Investigator considers the AE of concern to be specifically associated with AZD9291, dosing will be interrupted and supportive therapy administered as required in accordance with local practice/guidelines.

In cohort 1, if the toxicity resolves or reverts to \leq CTCAE grade 2 within 3 weeks of onset, treatment with AZD9291 may be restarted at the same dose. In cohort 2, if the toxicity resolves or reverts to \leq CTCAE grade 2 within 3 weeks of onset, treatment with AZD9291 may be restarted at the same dose (80 mg) or a lower dose (40 mg) using the rules below for dose modifications (Table 1) and with discussion and agreement with the AstraZeneca Study Team Physician as needed. There will be no individual modifications to dosing schedule in response to toxicity, only potential dose reduction or dose interruption.

If the toxicity does not resolve to \leq CTCAE grade 2 after 3 weeks, then the patient should be withdrawn from the study and observed until resolution of the toxicity.

Starting Dose	Reduced AZD9291 Dose
80 mg daily	40 mg daily
40 mg daily	no dose reduction

Table 1Dose interventions

On resolution of toxicity within 3 weeks:

• If an AE subsequently requires dose interruption, AZD9291 may restart at the same dose or the reduced dose (as per Table 1), on resolution/improvement of the AE at the discretion of the Investigator.

If new or worsening pulmonary symptoms (eg, dyspnoea) or radiological abnormality suggestive of interstitial lung disease is observed, an interruption in study treatment dosing is recommended, and the AstraZeneca study physician should be informed. A questionnaire regarding the results of the full diagnostic workup (including high-resolution computed tomography (HRCT), blood and sputum culture, haematological parameters) will be sent to Investigators. It is strongly recommended to perform a full diagnostic workup, to exclude

alternative causes such as lymphangitic carcinomatosis, infection, allergy, cardiogenic edema, or pulmonary hemorrhage. In the presence of confirmatory HRCT scans where other causes of respiratory symptoms have been excluded, a diagnosis of interstitial lung disease should be considered and study treatment permanently discontinued.

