In the absence of a diagnosis of interstitial lung disease study treatment may be restarted following consultation with the AstraZeneca Study Physician if the dosing interruption is no longer than 3 weeks.

Patients with QTcF prolongation fulfilling the following criteria (ie, confirmed QTcF prolongation to >500 msec absolute or a >60 msec increase from baseline) should have study treatment interrupted and regular ECGs performed until resolution to baseline. If the toxicity does not resolve to \leq grade 1 within 3 weeks the patient will be permanently withdrawn from study treatment.

Patients experiencing corneal ulceration or Interstitial Lung Disease (ILD) will not be permitted to restart study treatment.

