6.3.5 Laboratory safety assessment

Blood and urine samples for determination of clinical chemistry, haematology and urinalysis will be taken at the visits as indicated in the Study Plan (see Table 2). Laboratory tests do not need to be repeated at baseline if the baseline visit is within 7 days of the screening sample.

Blood and urine samples for safety assessment will be collected at the following times:

- Screening
- First dosing day (Day 1 Cycle 0); pre-dose (baseline)
- First day of multiple dosing, Day 1 Cycle 1; pre-dose
- Multiple dosing, Days 8 and 15 of Cycle 1; pre-dose

- On Day 1 of each subsequent cycle; pre-dose
- Discontinuation visit

The date of each collection will be recorded in the appropriate eCRF.

Following review of data from a group of patients the timing of blood samples may be adjusted for subsequent groups of patient. Additional sampling times may be added if indicated by the emerging data.

Laboratory values that meet the criteria for CTCAEv4 grade 3 or have changed significantly from baseline and are considered to be of clinical concern will be repeated/confirmed within 7 days and followed up as appropriate.

Clinical chemistry	Haematology
Serum (S)/Plasma (P)-Albumin	Blood (B)-Haemoglobin
S/P-ALT	B-Leukocyte
S/P-AST	B-Haematocrit
S/P-Alkaline phosphatase	B-Red blood cell (RBC) count
S/P-Bilirubin, total	B-Absolute leukocyte differential count
S/P-Calcium, total	Neutrophils
S/P-Creatinine	Lymphocytes
S/P-Glucose (fasting on PK days only)	Monocytes
S/P-Magnesium	Basophils
S/P-Potassium	Eosinophils
S/P-Sodium	B-Platelet count
S/P-Urea nitrogen	B-Reticulocytes
	Urinalysis
	U-Glucose
	U-Protein
	U-Blood

The following laboratory variables will be measured:

Additionally a urine/serum sample will be collected from all females of child bearing potential at screening, before first dose for a pregnancy test.

NB. In case a subject shows an AST or ALT $\geq 3x$ ULN and total bilirubin $\geq 2x$ ULN please refer to Appendix G 'Actions required in cases of combined increase of aminotransferase and total bilirubin-Hy's Law' for further instructions.

For blood volume see Section 6.6.1.

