6.4.3 Recording of adverse events

Time period for collection of adverse events

AEs will be collected throughout the study, from informed consent until the end of the follow up period. The follow-up period is defined as 28 days after study treatment is discontinued. SAEs occurring in the follow-up period should be reported to AstraZeneca in the usual manner (see Section 6.4.4).

Following discontinuation of AZD9291, SAEs considered related to study procedures should continue to be collected while patients are followed up for disease progression, as outlined in Table 3.

	Consent to Treatment Period	Until 28-day Follow- up Visit (safety follow-up period)	Post 28-day Follow-up visit
Collect all new AEs in eCRF	Yes	Yes	No
Collect all ongoing AEs in eCRF	Yes	Yes	No
Collect all study procedure- related SAEs in eCRF	Yes	Yes	Yes
Death due to AE, or unknown cause	Yes	Yes	No

Table 3 Summary of recording and follow-up of adverse events and deaths

After the final database lock, there may be some patients remaining on study treatment. For these patients who are continuing to receive AZD9291, AZ will collect information (during the treatment period and for 28 days after last dose) on SAEs, deaths (including those due to disease progression), discontinuation due to AEs/SAEs and drug accountability only.

Follow-up of unresolved adverse events

Any AEs that are unresolved at the patient's last visit (28-day follow-up visit) in the study are followed up by the investigator for as long as medically indicated. AstraZeneca retains the right to request additional information for any patient with ongoing AE(s) at the end of the study, if judged necessary.

If an investigator learns of any SAEs, including death, at any time after a patient has completed the study and he/she considers there is a reasonable possibility that the event is related to AZD9291, the investigator should notify AstraZeneca.

Variables

The following variables will be collected for each AE:

- AE diagnosis/description
- The date when the AE started and stopped
- Changes in CTCAE grade (for skin reactions and diarrhoea only); maximum CTCAE grade for all other AEs
- Whether the AE is serious or not
- Investigator causality rating against the investigational product (yes or no)

- Action taken with regard to investigational product
- Outcome

For SAEs other variables will be collected including treatment given for the event.

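### The toxicity bar to escalation from 40 to 80 mg names a grade 3 AE but omits 'or higher', so a resolved related grade 4 AE is not expressly barred

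*Protocol*

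**What the plan says.** Section 5.2 sets the conditions for escalation from 40 to 80 mg. The patient must have started on 40 mg and "have remained on treatment at a dose of 40mg for at least 6 months", have shown clinical benefit, and then have progressed by RECIST. The patient must also have had no treatment-related "grade 3 AE when treated at dose of 40mg, may have dose increased to 80mg after agreement in advance" between the Investigator and the sponsor's Study Physician. The toxicity condition carries neither 'or higher' nor a ≥ sign.

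Section 5.2.1 governs toxicity in the same patients. Dosing is interrupted for "CTCAE grade 3 or higher and/or unacceptable toxicity (any grade) not attributable to the disease" when the Investigator attributes the event to AZD9291. In Cohort 1, if the toxicity falls to grade 2 or lower "within 3 weeks of onset, treatment with AZD9291 may be restarted at the same dose. In cohort 2" (the closing words open the next sentence), the patient goes back to 40 mg. In Cohort 2, "treatment with AZD9291 may be restarted at the same dose (80 mg) or a lower dose (40 mg) using the rules below". Two conditions rule out restart whatever their course: "Patients experiencing corneal ulceration or Interstitial Lung Disease (ILD) will not be permitted to restart study treatment". Toxicity still above grade 2 after 3 weeks, and QTcF prolongation that does not resolve in that time, also end treatment.

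Section 6.4.3 collects changes in grade for skin reactions and diarrhoea, and the "maximum CTCAE grade for all other AEs".

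**The concern.** A toxicity criterion should become stricter as events become more severe. Taken at its words, and applied to the grade that the database holds, the Section 5.2 criterion does the reverse at the top of the scale. A patient whose worst related AE was grade 3 may not escalate, but one whose worst related AE was grade 4, resolved in time for restart, is not named.

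At stake is the eligibility rule for doubling a patient's dose. Such a rule is protocol content that a SAP would not normally define, and it should not depend on each site inferring what was meant.

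**Working it through.** The protocol gives no figure to reproduce on this point. The check is a reading of the sections together, followed by a day count to see whether the primary endpoint is affected.

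**Can the gap be reached?**

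1. A Cohort 1 patient has a related AE that peaks at grade 4. This meets the Section 5.2.1 threshold, and dosing stops.
2. The AE falls to grade 2 or lower within 3 weeks and is neither corneal ulceration nor ILD. Section 5.2.1 permits restart at 40 mg and makes no general exception for grade 4.
3. Unless the AE is a skin reaction or diarrhoea, Section 6.4.3 records it once, as grade 4.
4. The patient reaches 6 months on 40 mg with benefit and then progresses.
5. Section 5.2 asks about a related grade 3 AE, and none is on record. Escalation is therefore not expressly barred. With 'grade 3 or higher' it would be.

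**Does another section supply the missing words?** None does. The open-ended form appears elsewhere, with ≥3 for ocular events in Section 4.3, for diarrhoea in Section 5.2.3 and for the AE summaries in Section 7.7, but never in the escalation rule.

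**Two readings that would narrow the gap**

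- A grade 4 AE that falls to grade 2 may be said to have been experienced at grade 3 on the way down. Recorded grade changes could show this for skin reactions and diarrhoea, but the record would not show it for other AEs.
- Having remained on treatment for 6 months may be read to exclude anyone whose dosing was interrupted. Section 5.2 does not say so.

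The text settles neither.

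**Does it touch the primary PK endpoints?** Inputs are the visit schedule (Section 6.1, Table 2), the PK schedule (Section 6.5.1, Table 4), 21-day cycles, and the 6-month condition in Section 5.2.

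| Event | Calculation | Nominal study day |
|---|---|---|
| Cycle 0 Day 1 | start | 1 |
| Cycle 1 Day 1 | given | 8 |
| Cycle 2 Day 1 | 8 + 21 | 29 |
| Last scheduled PK sample (Cycle 2 Day 2) | 29 + 1 | 30 |
| End of Cycle 4, end of Part A | 8 + 4 × 21 − 1 | 91 |
| Earliest escalation | 6 × 365.25 / 12 = 182.6 days | about 183 |

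Six months is 182.6 / 21 = 8.7 cycles. The nominal gap between the last PK sample and the earliest escalation is 183 − 30 = 153 days. Sections 5.2 and 6.5.1 allow PK timing to move after missed doses or an interruption, so 30 is a nominal day and not a latest possible one. Section 3.1 confines PK to Part A and leaves Part B with safety and efficacy only. The primary PK endpoints are not affected.

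**The case against.** The strongest reply is that no competent physician would bar escalation after grade 3 and allow it after grade 4. The protocol itself uses a bare grade 3 as a floor in Section 6.3.5: "Laboratory values that meet the criteria for CTCAEv4 grade 3 or have changed significantly from baseline". On this view the text is loosely phrased, not wrong. Section 5.2 also asks what the patient experienced, not what the eCRF holds as a maximum, so bringing in the recording rule of Section 6.4.3 creates a gap that clinical judgement would close.

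Safeguards exist as well. Escalation is optional and needs advance agreement with the Study Physician, and dose interruptions are recorded. A grade 4 event that met a seriousness criterion would have reached the sponsor within 24 hours (Section 6.4.4). Finally, 80 mg is the Cohort 2 starting dose, and Section 5.2.1 lets Cohort 2 restart at 80 mg after a resolved toxicity of grade 3 or higher, which includes grade 4.

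Most of this stands and is why the point is minor. The intent is hardly in doubt and the practical risk is small. But evident intent and case-by-case agreement do not correct a written criterion. Section 5.2 chose a tighter toxicity condition for doubling the dose than Section 5.2.1 sets for resuming it, and its wording should deliver that condition.

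A ≥ sign lost when the PDF was read cannot be strictly excluded, but it would be speculation. Such signs survive in Sections 4.1, 4.3, 5.2.3 and 7.7 of the same copy.

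**Conclusion.** The point holds as a minor wording error in an operative dosing rule. Read literally by recorded maximum grade, Section 5.2 bars escalation after a related grade 3 AE and does not expressly bar it after a resolved related grade 4 AE. This rests on two assumptions: that the recorded grade is the one applied, and that an interruption followed by restart does not break the 6-month condition. If either fails, the gap narrows.

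Its reach is Cohort 1, about 12 patients, and within it only those who pass through every step from a related grade 4 AE to later progression. The protocol gives no rate of such events at 40 mg, so no probability is offered. There is no effect on the primary PK endpoints. The rule in Section 7.7 that AEs stay with the initial dose group after a dose modification is also unaffected.

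**What to change.** In Section 5.2, reword the toxicity condition to require that the patient had no treatment-related AE of CTCAE grade 3 or higher while on 40 mg. Do not carry over the any-grade unacceptable-toxicity limb of Section 5.2.1, because that would also bar escalation after grade 1 or 2 events.

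The cost is one phrase in the next amendment. Sample size, visits, PK endpoints and analysis do not change.

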5.2.1 Toxicity management

If a patient experiences a CTCAE grade 3 or higher and/or unacceptable toxicity (any grade) not attributable to the disease or disease-related processes under investigation, where the Investigator considers the AE of concern to be specifically associated with AZD9291, dosing will be interrupted and supportive therapy administered as required in accordance with local practice/guidelines.

In cohort 1, if the toxicity resolves or reverts to \leq CTCAE grade 2 within 3 weeks of onset, treatment with AZD9291 may be restarted at the same dose. In cohort 2, if the toxicity resolves or reverts to \leq CTCAE grade 2 within 3 weeks of onset, treatment with AZD9291 may be restarted at the same dose (80 mg) or a lower dose (40 mg) using the rules below for dose modifications (Table 1) and with discussion and agreement with the AstraZeneca Study Team Physician as needed. There will be no individual modifications to dosing schedule in response to toxicity, only potential dose reduction or dose interruption.

If the toxicity does not resolve to \leq CTCAE grade 2 after 3 weeks, then the patient should be withdrawn from the study and observed until resolution of the toxicity.

Starting Dose	Reduced AZD9291 Dose
80 mg daily	40 mg daily
40 mg daily	no dose reduction

Table 1Dose interventions

On resolution of toxicity within 3 weeks:

• If an AE subsequently requires dose interruption, AZD9291 may restart at the same dose or the reduced dose (as per Table 1), on resolution/improvement of the AE at the discretion of the Investigator.

If new or worsening pulmonary symptoms (eg, dyspnoea) or radiological abnormality suggestive of interstitial lung disease is observed, an interruption in study treatment dosing is recommended, and the AstraZeneca study physician should be informed. A questionnaire regarding the results of the full diagnostic workup (including high-resolution computed tomography (HRCT), blood and sputum culture, haematological parameters) will be sent to Investigators. It is strongly recommended to perform a full diagnostic workup, to exclude

alternative causes such as lymphangitic carcinomatosis, infection, allergy, cardiogenic edema, or pulmonary hemorrhage. In the presence of confirmatory HRCT scans where other causes of respiratory symptoms have been excluded, a diagnosis of interstitial lung disease should be considered and study treatment permanently discontinued.

In the absence of a diagnosis of interstitial lung disease study treatment may be restarted following consultation with the AstraZeneca Study Physician if the dosing interruption is no longer than 3 weeks.

Patients with QTcF prolongation fulfilling the following criteria (ie, confirmed QTcF prolongation to >500 msec absolute or a >60 msec increase from baseline) should have study treatment interrupted and regular ECGs performed until resolution to baseline. If the toxicity does not resolve to \leq grade 1 within 3 weeks the patient will be permanently withdrawn from study treatment.

Patients experiencing corneal ulceration or Interstitial Lung Disease (ILD) will not be permitted to restart study treatment.

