5.2.3 Diarrhoea

Recommendations for appropriate management of diarrhoea, including dose-adjustments for adverse events of diarrhoea that are of CTCAE grade \geq 3 or that are clinically significant and/or intolerable and considered by the investigator to be causally related to AZD9291, will be provided to investigators. Changes in CTCAE grade of diarrhoea will be captured in the AE eCRF.

5.2.4 **Duration of therapy**

Patients should continue on treatment with AZD9291 until discontinuation criteria is met. There is no maximum duration of treatment as patients may continue to receive AZD9291 beyond RECIST 1.1 defined progression as long as they are continuing to show clinical benefit, as judged by the investigator.

If AZD9291 is discontinued for any reason, the patient must complete all assessment at discontinuation visit specified in study plan (Table 2).

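### Section 5.2.1 ties restart after toxicity to cohort and starting dose, so on its natural reading a Cohort 1 patient escalated to 80 mg is not offered the step down to 40 mg that a Cohort 2 patient on 80 mg has

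*Protocol*

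**What the plan says.** **Escalation (Protocol Section 5.2).** A patient who started on 40 mg, stayed on it for at least 6 months and had no treatment-related grade 3 adverse event on it may move up. The patient must also "have shown clinical benefit (as judged by the investigator) and have then developed RECIST confirmed disease progression". Such a patient "may have dose increased to 80mg after agreement in advance between the Investigator and AZ Study Physician".

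**Restart after toxicity (Protocol Section 5.2.1).** Dosing is interrupted for drug-related toxicity that is grade 3 or higher or otherwise unacceptable. If it falls to grade 2 or lower within 3 weeks, the rule depends on cohort. For Cohort 1, and running into the start of the Cohort 2 rule, the text is "treatment with AZD9291 may be restarted at the same dose. In cohort 2, if the toxicity resolves or reverts to" that grade in the same period, treatment "may be restarted at the same dose (80 mg) or a lower dose (40 mg) using the rules below for dose modifications (Table 1"), "with discussion and agreement with the AstraZeneca Study Team Physician as needed".

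**Table 1.** The first column is headed by starting dose. The 80 mg row leads to 40 mg daily; the 40 mg row allows no reduction.

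**Later interruptions (bullet under Table 1).** "AZD9291 may restart at the same dose or the reduced dose (as per Table 1), on resolution/improvement of the AE", at the investigator's discretion.

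**Schedule changes (Section 5.2.1).** "There will be no individual modifications to dosing schedule in response to toxicity, only potential dose reduction or dose interruption".

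**The concern.** The escalation path creates a patient who belongs to Cohort 1, started on 40 mg and now takes 80 mg. Section 5.2.1 and Table 1 are organised by cohort and by starting dose, and both assume that these identify the dose being taken. For an escalated patient they do not.

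At stake is what a site may do when such a patient has a resolved toxicity on 80 mg. Individual schedule changes are barred, so for a patient who restarts, dose reduction is the only individual way to lower exposure. It is also the option that the Cohort 1 sentence does not name. Sites can read that sentence and Table 1 differently and so handle the same situation differently.

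**Working it through.** The protocol states no figure on this point. The check is to apply the rules to each kind of patient and then to see whether the situation can arise.

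**1. Cohort does not change on escalation.** Section 3.1 makes the first 12 patients enrolled the 40 mg cohort. Section 5.2 describes escalated patients as having started on 40 mg. An escalated patient is therefore still in Cohort 1, with starting dose 40 mg.

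**2. Rules applied side by side**, for toxicity at grade 2 or lower within 3 weeks:

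| | Cohort 1, escalated | Cohort 2, not reduced |
|---|---|---|
| Starting dose | 40 mg | 80 mg |
| Dose at toxicity | 80 mg | 80 mg |
| Cohort sentence | same dose (80 mg) | 80 mg or 40 mg |
| Table 1, by starting dose | no reduction | 40 mg |
| Table 1, if read as current dose | 40 mg | 40 mg |

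By starting dose, the cohort sentence and Table 1 agree for the escalated patient: no step-down. By current dose, Table 1 gives 40 mg but the Cohort 1 sentence names only the same dose. The bullet on later interruptions refers back to Table 1, so it settles nothing.

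**3. Other provisions.** Interstitial lung disease, corneal ulceration and toxicity unresolved at 3 weeks are handled alike in both cohorts. Sections 5.2.2 and 5.2.3 promise separate dose-adjustment guidance for skin reactions and diarrhoea; its content is not in the protocol. Other restartable toxicities rest on Section 5.2.1.

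**4. Reach.** At most the 12 or so patients of Cohort 1, out of about 24. The protocol gives no rate of escalation or of toxicity after it, so no expected number can be derived.

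**5. Timing against PK sampling.** Cycle 1 Day 1 is study day 8, so Cycle 2 Day 2, the last PK sample, is nominally 8 + 21 + 1 = day 30. Six months is about 183 days. Escalation therefore comes at least about 183 − 30 = 153 days after the last PK sample.

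**6. Can it happen before the second data cut-off?** Scans fall on days 8 + 42k: 50, 92, 134, 176, 218, 260, 302 (each ±7). The first nominally past 6 months is day 218. The second cut-off is 12 months after the last patient's first dose if anyone is still on treatment. So the situation can arise within the reported period.

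**The case against.** The strongest reply is that the restriction is inferred. The Cohort 1 sentence is permissive and contains no word of exclusion. It was probably written with patients on 40 mg in mind, for whom the same dose is the only choice. The general sentence on dose reduction and the bullet under Table 1 name no cohort, and a site with a patient on 80 mg could reasonably use the 80 mg row. This stands to the extent that the protocol does not expressly forbid the step-down. It does not remove the problem: the contrast between the two cohort sentences and the 40 mg row both point the other way, and nothing else in the protocol settles it.

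A second reply is that the omission may be deliberate, because stepping down returns the patient to a dose on which the tumour progressed. That is a fair clinical argument, but the protocol does not make it. Section 5.2.4 allows treatment beyond progression "as long as they are continuing to show clinical benefit, as judged by the investigator". That does not show 40 mg is suitable for an escalated patient, but it does not rule it out.

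A reader might infer that the two patients on 80 mg differ only in starting dose. They do not: the escalated patient has progressed on 40 mg, and the Cohort 2 patient need not have.

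A reader might also infer from the scan calendar a guaranteed minimum time on 80 mg before the cut-off. The documents give none. Taking 365 days as the earliest cut-off for a patient still treated, progression at the day 218 scan leaves 365 − 218 = 147 days, but progression first seen at day 302 leaves 365 − 302 = 63.

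**Conclusion.** The point holds as a minor dosing-safety inconsistency. A stated rule does not fit a path that the protocol itself allows: on one reading of Table 1 an escalated patient has no written step-down, and on the other the table conflicts with the Cohort 1 sentence.

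The consequence is small. Escalation has several conditions, so probably few patients are concerned. Restart is optional, so nobody is forced back onto 80 mg, and the sponsor's physician already knows each escalated patient. The primary PK analysis and response before escalation are unaffected.

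The conclusion assumes that cohort membership stays as set at enrolment, and that the unseen skin and diarrhoea guidance does not rewrite the general rule. A reader might go further and infer that the protocol prohibits reduction or compels re-exposure at 80 mg; the text supports neither.

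**What to change.** Head the first column of Table 1 'Dose at time of toxicity' and keep its two rows. Replace the two cohort sentences with one rule by current dose. After resolution to grade 2 or lower within 3 weeks, any patient taking 80 mg, including a Cohort 1 patient escalated under Section 5.2, may restart at 80 mg or 40 mg per Table 1, with the existing wording on Study Team Physician agreement kept. A patient taking 40 mg may restart at 40 mg. Add that for escalated patients the step-down is optional and depends on continuing clinical benefit as judged by the investigator.

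The cost is one column heading and a sentence or two in an amendment, with no extra patients, visits or procedures. Cohort 2 patients on 80 mg are handled as now. There is one side effect: a Cohort 2 patient already reduced to 40 mg would restart at 40 mg, whereas the present sentence names 80 mg as the same dose for the whole cohort. If the sponsor prefers not to touch Cohort 2, a single sentence covering escalated patients would close the gap. The clinical downside is that a few patients may return to a dose on which their tumour had progressed.
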